3.9 Screen Failures

A screen failure subject is one from whom informed consent is obtained and is documented (ie, subject signs an ICF), but who is withdrawn from this study before being randomized.

For any subject to whom screen failure applies, the following items will be recorded in the CRF:

- Subject identification number
- Date of informed consent
- Date of visit (date of screening examination)
- Subject background survey (date of survey, date of birth, sex, race, ethnicity)
- Assessment result for eligibility criteria
- Date of assessment of screen failure
- Reason for assessment of screen failure

3.10 Definition of Completed Subjects

The treatment period is defined as the time period during which subjects are evaluated for trial objectives irrespective of whether or not the subject actually consumes all doses of IMP. Subjects who are evaluated at the last scheduled visit during the trial period will be defined as trial completers. For purposes of this trial, subjects who complete Day 54 will be defined as trial completers.

3.11 Definition of Subjects Lost to Follow-up

Subjects with whom contact is lost during the trial period and subjects who do not have a known reason for discontinuation (eg, withdrew consent or AE, etc.) will be classified as lost to follow-up.

The investigator or subinvestigator, or designee will make 3 documented attempts to contact the subject by telephone and in the event the site is unable to reach the subject by

telephone, the investigator or subinvestigator, or designee will attempt to contact the subject via certified mail or an alternative similar method where appropriate, before assigning a "lost to follow-up" status. When a subject is lost to follow-up, presence/absence of contact with the subject, date of contact, and contact method will be recorded in the CRF.

3.12 Subject Compliance

The date and time of each trial drug administration, dosage form, and use or non-use of water when taking medication will be recorded in the source documents and CRF. Information regarding any missed or inappropriately administered doses will also be documented in the source document and in the CRF.

3.13 Protocol Deviations

In the event of a major deviation from the protocol due to an emergency, accident, or mistake (eg, IMP dispensing or subject dosing error or violation of concomitant medication criteria), the investigator or subinvestigator, or designee will contact the sponsor at the earliest possible time by telephone. The investigator or subinvestigator, medical expert, and sponsor will come to a joint decision as quickly as possible regarding the subject's continuation in the trial. If the decision reached is to allow the subject to continue in the trial, this must be documented by the investigator or subinvestigator, and the sponsor, and approved by the medical expert. All deviations from the written protocol should be recorded in the source documents by the investigator or subinvestigator. If a significant deviation occurs, the date of occurrence of significant deviation and its summary should be recorded in the CRF.

4 Restrictions

4.1 Prohibited Medications

No medications other than planned IMP may be taken during the trial.

- From 14 days before the first IMP administration until completion of follow-up Prescription medications, OTC medications, herbal medication, vitamin supplements
- From 30 days before the first IMP administration until completion of follow-up Antibiotics

Exceptions to the above may be allowed only in cases where the sponsor judges that administration of the drug is unlikely to influence the pharmacokinetics of brexpiprazole. Exceptions must be discussed with the sponsor on a case-by-case basis and reasons documented.

4.2 Other Restrictions

The following will be prohibited during the specified period.

- From 14 days before the first IMP administration until completion of blood sampling on Day 54 (312 hours postdose in Period 3)
 - Food or beverages containing St. John's Wort
- From 72 hours before the first IMP administration until completion of blood sampling on Day 54 (312 hours postdose in Period 3)
 - Grapefruit, grapefruit products, Seville oranges, Seville orange products, star fruit, or star fruit products
- From 72 hours before each administration until discharge at the end of each hospitalization period
 Alcohol
- During hospitalization
 - Food or beverages containing methylxanthines (such as caffeinated coffee, caffeinated tea, caffeinated soda, and chocolate)
- From 2 months before screening until completion of follow-up Smoking
- From the time of informed consent until completion of follow-up Blood donation

5 Reporting of Adverse Events

5.1 Definitions

An AE is defined as any untoward medical occurrence in a clinical trial subject administered a medicinal product and which does not necessarily have a causal relationship with this treatment. Adverse events would not include information recorded as current symptoms at screening for preplanned procedures for which the underlying condition was known and no worsening occurred.

An adverse reaction is any untoward and unintended response to an IMP related to any dose administered.

A suspected adverse reaction is any AE for which there is a reasonable possibility that the IMP caused the AE.

An SAE includes any event that results in any of the following outcomes:

- Death
- Life-threatening; ie, the subject was, in the opinion of the investigator or subinvestigator, at immediate risk of death from the event as it occurred. It does not include an event that, had it occurred in a more severe form, might have caused death.
- Persistent or significant incapacity/disability
- Requires inpatient hospitalization or prolongs hospitalization
 - Hospitalization itself should not be reported as a serious treatment-emergent adverse event (TEAE); whenever possible the reason for the hospitalization should be reported.
 - Hospitalizations or prolonged hospitalizations for social admissions (ie, those required for reasons of convenience or other nonmedical need) are not considered serious TEAEs.
- Congenital anomaly/birth defect.
- Other medically significant events that, based upon appropriate medical judgment, may jeopardize the subject and may require medical or surgical intervention to prevent one of the outcomes listed above, eg, allergic bronchospasm requiring intensive treatment in an emergency room or home, blood dyscrasias or convulsions that do not result in hospitalization, or the development of drug dependency or drug abuse.

Nonserious AEs are all AEs that do not meet the criteria for a "serious" AE.

Immediately Reportable Event (IRE):

- Any SAE
- Any AE related to occupational exposure.
- Potential serious hepatotoxicity (see Section 5.4 Potential Serious Hepatotoxicity).
- Pregnancy. Although normal pregnancy is not an AE, it will mandate IMP
 discontinuation and must be reported on an IRE form to the sponsor. Pregnancy will
 only be documented on the AE CRF if there is a complication or abnormality in the
 newborn. The above includes pregnancy occurring in female partners of male subject.

Clinical Laboratory Assessment Value Changes: It is the investigator's or subinvestigator's responsibility to review the results of all laboratory tests as they become available. This review will be documented by the investigator's or subinvestigator's dated signature on the laboratory report. For each abnormal laboratory test result, the investigator or subinvestigator needs to ascertain if this is an abnormal (ie, clinically relevant) change from baseline in each period for that individual subject. This

determination, however, does not necessarily need to be made the first time an abnormal value is observed. The investigator or subinvestigator may repeat the laboratory test or request additional tests to verify the results of the original laboratory tests. If this laboratory value is considered clinically relevant by the investigator or subinvestigator (eg, subject is symptomatic, requiring corrective treatment or further evaluation), or if the laboratory value leads to discontinuation, or fulfills a seriousness criterion, this is considered an AE.

Severity: Adverse events will be graded on a 3-point scale.

1 = Mild: Discomfort noticed, but no disruption to daily activity.

2 = Moderate: Discomfort sufficient to reduce or affect normal daily activity.

3 = Severe: Inability to work or perform normal daily activity.

IMP Causality: Assessment of causal relationship of an AE to the use of IMP:

Related: There is a reasonable possibility of a temporal and causal

relationship between the IMP and the AE.

Not Related: There is no temporal or reasonable relationship between the IMP and

the AE.

5.2 Eliciting and Reporting Adverse Events

The investigator or subinvestigator will assess subjects for the occurrence of AEs. For this trial, information on AEs will be followed until the end of the trial as specified in Section 3.7.6. To avoid bias in eliciting AEs, subjects should be asked the non-leading question: "How are you feeling?" All AEs (serious and nonserious) reported by the subject must be recorded in the source documents and CRFs provided by the sponsor. The source documents and CRF are to include event name, date and time of onset (recording of time of day is necessary for vomiting and wherever possible for other AEs), date of recovery, seriousness, severity, IMP causality, action taken regarding IMP administration, and outcome. All AE and SAE collections are to begin after a subject has signed the ICF and will continue until the last scheduled contact.

Use medical terminology in AE reporting. Adverse events should be reported as a single unifying diagnosis whenever possible or, in the absence of a unifying diagnosis, as individual signs or symptoms. Exacerbation or disease progression should be reported as

an AE only if there are unusual or severe clinical features that were not present, or experienced earlier, or not expected based on the course of the condition.

If there is any change in the severity or seriousness of an AE that has been reported, the AE must be reported as a new AE in the CRF.

In addition, the sponsor must be notified immediately by e-mail, as a rule, of any IREs according to the procedure outlined below in Section 5.3 Immediately Reportable Events. Special attention should be paid to recording hospitalization and concomitant medications

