3.2.2 Treatment Period

After single oral administration of the Period 1 IMP, there will be a washout period of 20 days, after which subjects will receive single oral administration of the Period 2 IMP (a different combination of drug formulation and administration method than that of Period 1). After single oral administration of the Period 2 IMP, there will be another washout period of 20 days, after which subjects will receive single oral administration of the Period 3 IMP (a different combination of drug formulation and administration method than those of Period 1 and Period 2).

[Rationale for treatment period]

According to the BE Guideline,¹¹ studies should be conducted based on single dosing, as a rule.

[Rationale for washout period]

From the results of a Japanese single-dose trial (331-07-002), the mean elimination half-life of brexpiprazole was 66.6 hours in the 4 mg treatment group, for which the elimination half-life was longest. According to the BE Guideline, "Washout periods

should usually be more than 5 times the elimination half-life of the unchanged active ingredient or active metabolites to be measured." This suggests that the washout period should be more than 333 hours (more than 14 days), which is 5 times the elimination half-life. The results of the Japanese bioequivalence study (331-10-005) showed that the blood drug concentration prior to the dosing for Period 2 after a washout period of 20 days was less than 5% of C_{max} in all subjects, and therefore the washout period following trial drug administration is set to be 20 days.

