3.7.4 Safety Assessments

3.7.4.1 Adverse Events

Refer to Section 5 Reporting of Adverse Events for the methods and timing for assessing, recording, and analyzing AEs. This trial is a crossover study, and AEs in each period will be assessed based on a comparison with the subject's status before the IMP administration in the respective periods.

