9.2 Adverse Events

Medical Dictionary for Regulatory Activities (MedDRA) version 22.0 will be used to code AEs. TEAEs in each period are defined as adverse events occurred on or after the IMP administration in each period to before the IMP administration in next period or the end of study. If multiple occurrences of the same event are observed in the same subject during the same period, the highest severity will be used for analysis.

The incidence of the following events will be summarized by system organ class, preferred term (the denominators will be subjects who administered by each formulation and administration method).

- TEAEs
- TEAEs by severity

The incidence of the following events will be summarized (the denominators will be subjects who administered by each formulation and administration method).

- TEAEs with an outcome of death
- Serious TEAEs
- TEAEs leading to discontinuation of the IMP

TEAEs potentially causally related to the IMP will also be summarized in the same way.

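### Read literally, the new-record rule in Protocol 5.2 and the timing-only TEAE rule in SAP 9.2 can count an event that eases after a dose as a TEAE of that dose's formulation, contrary to Protocol 3.7.4.1

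*Protocol*

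**What the plan says.** Three provisions bear on the point.

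- **Recording (Protocol 5.2).** The rule for CRF entries is that, upon "any change in the severity or seriousness of an AE that has been reported, the AE must be reported as a new AE". The sentence is not limited to worsening. The same section starts AE collection at signing of consent and lists date and time of onset among the items recorded for an AE. On severity, Protocol 5.1 says "Adverse events will be graded on a 3-point scale" (mild, moderate, severe).
- **Attribution (SAP 9.2).** "TEAEs in each period are defined as adverse events occurred on or after the IMP administration in each period", running to the next period's dose or the end of the study. There is no condition that the event be new or worse than before the dose. Repeats are handled by one rule: "If multiple occurrences of the same event are observed in the same subject during the same period, the highest severity will be used". Incidence is taken over the subjects given each formulation and administration method.
- **Assessment (Protocol 3.7.4.1).** Because this is a crossover, "AEs in each period will be assessed based on a comparison with the subject's status before the IMP administration in the respective periods".

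Neither Protocol 5.2 nor SAP 9.2 refers to the comparison in 3.7.4.1, and neither document says which rule governs when they disagree.

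**The concern.** A milder continuation of something the subject already had before dosing is an improvement on predose status. Under 3.7.4.1 it should not count against the treatment just given. Yet 5.2 turns the improvement into a new AE, and SAP 9.2 then asks only when that AE occurred. The highest-severity merge does not help, because it works inside one period and the two records lie on either side of a dose.

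At stake is the safety comparison itself: TEAE incidence by formulation and administration method (SAP Appendix 1, tables CT-8.2.1 and CT-8.2.2, and the IMP-related tables CT-8.3.1 and CT-8.3.2 if the new record is judged related). An event that began under one treatment, or before any treatment, could be added to the count of another.

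**Working it through.** The plan states no figure to reproduce. The check applies the two rules literally to short event histories, then sizes the effect of one affected subject.

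**Inputs.** Doses on Days 1, 21 and 41 (Protocol 3.1); new record at each change of grade (Protocol 5.2); period set by when the record occurs, with highest severity within a period (SAP 9.2); 21 planned subjects, 18 required for power (Protocol 7.1). Assumption: the new record is dated at the change. Protocol 5.2 does not say so outright.

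**Event histories**

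| History | Literal 5.2 + SAP 9.2 | Against predose status (3.7.4.1) |
|---|---|---|
| A. Moderate from Day 15, grade unchanged, ends Day 25 | Period 1, moderate | Period 1 only: agrees |
| B. Moderate Day 15, mild from Day 18, ends Day 25 | Period 1, moderate | Period 1 only: agrees |
| C. Moderate Day 15, mild from Day 23, ends Day 25 | Period 1, moderate **and** Period 2, mild | Period 1 only: **conflict** |
| D. Moderate Day 2, mild from Day 4 | Period 1, moderate, counted once | Period 1 only: agrees |
| E. Moderate after consent and before Day 1, mild after the Day 1 dose | Period 1, mild | Not an AE of Period 1: **conflict** |

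The conflict needs all three of: the event is present before the dose, it is still ongoing at the dose, and its grade falls on or after the dose. Crossing a dosing day is not enough (A), nor is a fall in grade before the dose (B). Full recovery is captured as a recovery date and outcome, and 5.2 does not describe it as a change in severity.

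**Size of one case.** Effect on an arm's incidence = 1/n.

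- n = 21: 1/21 = 4.8 percentage points.
- n = 18: 1/18 = 5.6 percentage points.

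For scale, the AE incidences in the earlier 4-mg ODT study (Protocol 1.2.2, a different ODT formulation) were 52.9%, 38.9% and 50.0%, a spread of 52.9 − 38.9 = 14.0 points. One subject in 21 is about a third of that spread (4.8/14.0 = 0.34).

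**Opportunities.** 21 × 3 = 63 planned dosing times. At the 21 on Day 1 there is no earlier formulation, so only history E can arise. At the other 63 − 21 = 42, an event can shift between formulations as in C. How many would do so cannot be estimated, because the documents give no AE durations. Protocol 3.2.2 sets a 20-day washout after the first dose, and after the second "there will be another washout period of 20 days", so the number should be small.

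**The case against.** The strongest reply is that the governing principle is already written. Protocol 3.7.4.1 compares each period with its own predose status, and Protocol 5.1 defines an AE as an untoward occurrence. Read with these, a milder continuation is not an AE of the new period, and SAP 9.2 needs at most a cross-reference. This narrows the point without removing it. SAP 9.2 states its own complete definition, does not invoke 3.7.4.1, and is the text from which the tables will be programmed.

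Second, the date carried by the new record is inferred, and SAP 9.2 speaks of events that occurred, not of onset dates. That stands as a stated assumption. If a site instead carried the first onset date forward, histories C and E would not be miscounted. But a genuine worsening after the dose would then stay with the earlier period, so the attribution rule would still need stating.

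Third, safety is descriptive, no decision rule depends on TEAE incidence, and 4.8 points is simply one subject in 21. All true; the figure gives the size of a case, not its likelihood.

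A reader might go further than the documents allow in three ways:

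- **That any resolving event crossing a dosing day moves to the next formulation.** Histories A and B show that it does not.
- **That a step down from serious to nonserious will often be charged to the next formulation.** Protocol 3.8.3.2 lists an SAE under the undue-risk grounds for withdrawal, and 3.8.3.1 ends participation when treatment is discontinued. The case is largely hypothetical.
- **That AE durations and outcomes will be analysed wrongly.** No planned table analyses AE duration. Splitting an event into dated records makes the AE listing longer, which is not in itself an error.

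**Conclusion.** The concern holds in a limited form. Three stated rules do not fit together, and literal use of two of them gives an attribution that the third rejects. The result is a possible overcount of about 4.8 points in one arm's TEAE incidence per affected subject (5.6 points if only 18 subjects are dosed in that arm). It is confined to events present before a dose and still ongoing whose grade falls on or after that dose. It rests on SAP 9.2 being programmed as written and on the new record being dated at the change of grade.

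Cases should be few. Repeat records within one period do not inflate incidence, because each subject's event is counted once at its highest severity. The bioequivalence conclusion on Cmax and AUCt is untouched. The change is still worth making, since the fault lies in stated rules and the remedy is very cheap.

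**What to change.** **In SAP 9.2**, add that an event already present before a period's dose counts as a TEAE of that period only if it worsens in severity or becomes serious on or after that dose, and that a re-recorded improvement of such an event is not a new TEAE. This carries the comparison in Protocol 3.7.4.1 into the analysis and still counts genuine worsening. The cost is this short addition and the matching programming. It needs no extra data, and Protocol section 7 allows the SAP to be settled up to data lock.

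**Optionally, in Protocol 5.2**, either limit the new-record rule to worsening (an increase in severity, or becoming serious), or keep it and link each continuation record to the original event and its onset date. Limiting the rule has a small downside: the time course of improvement is no longer held in separate records. Linking keeps that detail and makes the SAP rule easier to program. Neither is needed to settle attribution once the SAP text is in place.

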5.3 Immediately Reportable Events

The investigator or subinvestigator, or designee must report any SAE, any AE related to occupational exposure, potential serious hepatotoxicity, or confirmed pregnancy, by email to the sponsor, immediately after either the investigator or subinvestigator become aware of the event. An IRE form or other form should be completed and sent by e-mail, in principle, to the sponsor using the contact information on the title page of this protocol. (Please note that the IRE form is a specific form provided by the sponsor and is NOT the AE CRF.)

Subjects experiencing SAEs or IREs should be followed clinically as described in Section 5.7.2. It is expected that the investigator or subinvestigator will provide or arrange appropriate supportive care for the subject and will provide prompt updates on the subject's status to the sponsor.

5.4 Potential Serious Hepatotoxicity

For a subject who experiences an elevation in aspartate aminotransferase (AST) or alanine aminotransferase (ALT) that is ≥ 3 times the upper limit of normal (ULN), a total bilirubin level should also be evaluated. If the total bilirubin is ≥ 2 times the ULN, complete an IRE form or other form with all values listed and also report as an AE on the CRF.

5.5 Pregnancy

Women of childbearing potential are women whose menstruation has started and who are not documented as sterile (eg, have had a bilateral oophorectomy, or hysterectomy, or who have been postmenopausal for at least 12 months).

For sexually active subjects with partners who are women of childbearing potential, there must be a documented agreement that the subject and their partner will take effective measures (ie, 2 different approved methods of birth control or remains abstinent) to

prevent pregnancy during the course of the trial and for 30 days after the last dose of IMP. Unless the subject or subject's partner is sterile (ie, women who have had a bilateral oophorectomy, have had a hysterectomy, or have been postmenopausal for at least 12 consecutive months; or men who have had a bilateral orchidectomy) or remains abstinent during the trial and for 30 days after the last dose of IMP, 2 of the following approved methods of birth control must be used: vasectomy, tubal ligation, intrauterine device, birth control pills, condom with spermicide, or occlusive cap (vaginal diaphragm or cervical/vault cap) with spermicide. Any single method of birth control, including vasectomy and tubal ligation, may fail, leading to pregnancy. The contraceptive method will be documented in the CRF. Male subjects must also agree not to donate sperm from trial screening through 30 days after the last dose of IMP.

Before enrolling subjects in this clinical trial, investigators or subinvestigators must review the below information about trial participation as part of the ICF process. The topics should generally include:

- General information
- Informed consent form
- Pregnancy prevention information
- Contraceptives in current use
- Follow-up of a reported pregnancy

Before trial enrollment, subjects must be advised of the importance of avoiding pregnancy during trial participation and the potential risk factors for an unintentional pregnancy. Subjects must sign the ICF confirming that the above-mentioned risk factors and the consequences were discussed.

During the trial, all subjects should be instructed to contact the investigator or subinvestigator immediately if they suspect their partners might be pregnant (eg, missed or late menstrual cycle).

The investigator or subinvestigator must immediately notify the sponsor of any pregnancy associated with IMP exposure during the trial and for 30 days after the last dose of IMP, and record the event on the IRE form and forward it to the sponsor. The sponsor will forward the Pregnancy Surveillance Form(s) to the investigator or subinvestigator for monitoring the outcome of the pregnancy.

Protocol required procedures for trial discontinuation and follow-up must be performed on the subject. Other appropriate pregnancy follow-up procedures for a subject's partner should be considered if indicated. In addition, the investigator or subinvestigator must report to the sponsor, on the Pregnancy Surveillance Form(s), follow-up information regarding the course of the pregnancy, including perinatal and neonatal outcome. Infants will be followed for a minimum of 6 months from the date of birth.

